## 10 Analysis Methods

### OVERVIEW OF THE ANALYSIS

The analyses to be conducted in this study will include Demography, Baseline Characteristics, Safety and Tolerability, and EBA.

#### 10.1 Demography, Safety, and Baseline Characteristics

The disposition of participants, completion of the study, and reasons for withdrawal will be summarised by treatment and overall. The number of participants withdrawing and the reason for withdrawal will also be summarised by the last treatment taken.

In the event of more than a single data point (for a particular variable) prior to the administration of trial medication, “baseline” will be regarded as the first of these observations.

Demographic data will be summarised by treatment and overall. Summary statistics will be calculated for age, race and gender, height, weight, and body mass index (BMI) for the Safety Population.

Substance use of the safety population will also be summarised by treatment and overall.

The results of the medical history (refer to Adverse Events for an explanation regarding the coding of medical history), vital signs, safety laboratory values, and physical examination at baseline/screening will be tabulated by treatment for the Safety Population.

Prior medication is defined as any medication that ended prior to the first dose of trial medication. Incidence will be summarised by generic name and class by dose for the Safety Population.

Listings for the data used in the tabulations will also be given. Listings containing the following information will also be included:

1. Study Completion Status
2. Visit Dates (including hospital admission and discharge)
3. Eligibility and Inclusion and Exclusion Criteria
4. Subject Eligibility (including Informed Consent, Initial Diagnosis and Randomization)
5. Urine Drug Screen
6. Serum Pregnancy
7. Serology (HIV) and CD4 Count
8. Study Drug Administration (including compliance)
9. Adverse Events
10. Physical Examination
11. Vital Signs
12. Chest X-ray

The response to the eligibility assessments and inclusion/exclusion criteria will be listed.

For each treatment exposure (EX), the dose/number of tablets/capsules (group dependent) taken overall will be calculated along with the percent compliance out of the total number of

tablets/capsules expected and will be summarised by dose for the Safety Population.

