	
kanamycin, pyrazinamide, para-aminosalicylic acid, rifapentine, thioacetazone, capreomycin, thioamides].
 
11. Treatment with immunosuppressive medications such as TNF-alpha inhibitors within 2 weeks prior to screening, or systemic corticosteroids for more than 7 days within 2 weeks prior to screening.
 
12. Treatment with nitric oxide and other nitric oxide donor agents (e.g., prilocaine, sodium nitroprusside and nitro-glycerine), phosphodiesterase inhibitors (e.g., sildenafil) and lung surfactant drugs (e.g., beractant, calfactant, poractant), within 30 days prior to screening.
 
Laboratory Safety Testing
 
13. Participants with the following toxicities at screening as defined by the enhanced Common Terminology Criteria for Adverse Events (CTCAE) toxicity table version 5.0, 27Nov2017 (
 
14. Appendix 1)
 
(a) creatinine >1.5 times upper limit of normal (ULN)(b) haemoglobin <8.0 g/dL(c) platelets <50x10⁹ cells/L(d) serum potassium <3.0 mmol/L(e) aspartate aminotransferase (AST) >3 x ULN(f) alanine aminotransferase (ALT) >3 x ULN(g) alkaline phosphatase (ALP) ≥ 2.5 x ULN(h) total bilirubin >1.5 x ULN(i) total white cell count <2 cells x 10⁹/L. 
NOTE: Investigations may be repeated once during screening if the initial result is unfavourable.

Study Duration	
Participants who complete the study will participate for a maximum of 37 days (screening period of up to 9 days, followed by a treatment period of 16 days and a follow-up visit at Day 28 from first dose of IMP).
 
The overall duration of participants involvement in the study is planned to be approximately 1.5 years (first participant in to last participant out, including the pause between stages 1 and 2 for the interim analyses and continuation decision).

Sample Size	
This is a proof-of-concept study without hypothesis testing. The planned sample size of 15 participants per treatment group is in keeping with other phase 2 studies of this type and accounts for the possibility of up to 3 dropouts per arm which represents a conservative estimate of the expected drop-out rate. Previous EBA studies indicate that a sample size of 12 participants per arm allowed for the identification of proof-of-concept i.e., change in TTP/CFU compared to no change in TTP/CFU for all evaluated arms.

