Secondary: Safety and tolerability	To determine the safety and tolerability of inhaled RESP301 6 mL via NEB administered qd, bd, and tds alone, or tds in combination with HRZE, over 14 days of treatment.	Measurement of: 
 • Adverse Events • Concomitant Medication • Safety Laboratory (Haematology, Chemistry, Urinalysis) • Methaemoglobin • Physical Examinations • Vital Signs • Body Mass Index (BMI). 	Incidence of Treatment Emergent Adverse Events (TEAEs) will be presented by severity, drug relatedness, seriousness, leading to early withdrawal and leading to death. Clinical laboratory measurements and vital signs will be summarized using descriptive statistics as actual values and changes from baseline. Physical examinations and concomitant medications will be listed.
Exploratory	To explore the EBA variability due to potential M.tb sterilisation in sputum samples as a result of NO contamination in sputum samples.	Overnight sputum collection from which viable mycobacteria in the sample is quantified as TTP using the MGIT (BactecTM MGIT™ 960) system.	Comparison of EBA _{TTP} (0-14) versus EBA _{TTP} (0-15) and the predicted EBA _{TTP} (14-15) versus observed EBA _{TTP} (14-15) analysed using linear and non-linear functions using mixed effects modelling of TTP over time and analysis of variance.

1.3. Study Flow Chart for Stages 1 and 2

Period	Screening			Treatment															FU 20 ^A	EWD	
	Visit 1	2	3	4	5	6	7	8	9	10	11	12	13	14	15	16	17	18	19		
Day (-9 to -3)	-2	-1	1	2	3	4	5	6	7	8	9	10	11	12	13	14	15	16	28		
Written Informed Consent	X																				
Demography	X																				
Medical & Treatment History	X																				
Physical Examination ^{B, C}	X			X	X	X	X	X	X	X	X	X	X	X	X	X	X	X	X	X	
Vital Signs ^C	X	X	X	X	X	X	X	X	X	X	X	X	X	X	X	X	X	X	X	X	
Height	X																				
IMP Administration ^D , and Compliance Check				X	X	X	X	X	X	X	X	X	X	X	X	X	X	X	X		
Concomitant Medication ^E	X	X	X	X	X	X	X	X	X	X	X	X	X	X	X	X	X	X	X	X	
Adverse Events ^F				X	X	X	X	X	X	X	X	X	X	X	X	X	X	X	X	X	
Eligibility Assessment ^G		X																			
EBA unit inpatient	X ^H	X	X	X	X	X	X	X	X	X	X	X	X	X	X	X	X	X	X ^I		
Randomisation ^J		X																			
Chest X-ray		X																			
Spot or Overnight Sputum ^{K, L}	X																				
Overnight Sputum ^{K, M}		X	X	X	X	X	X	X	X	X	X	X	X	X	X	X	X	X			
Safety labs (Haematology, Chemistry, Urinalysis) ^C	X			X								X								X	X
Methaemoglobin (SpMet) ^N	X			X								X								X	

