Coagulation Blood Screen	X																				
HIV Test and CD4 Count	X																				
Urine Drug Screen	X																				
β-HCG Serum Pregnancy Test ^O	X																				X

EBA: Early bactericidal activity, EWD: Early withdrawal, FEV1: Forced Expiratory Volume in the first second, FU: Follow-up; IMP: Investigational Medicinal Product

- A: Follow-up visit: a window of ± 3 days allowed.
- B: Physical examinations: Full will be complete at screening and targeted (symptom-directed) thereafter.
- C: Vital signs, safety laboratory: on days where there is IMP dosing, to be performed pre-dose.
- D: IMP administration: The HRZE is to be administered fasted (1 hour before, or 2 hours after food) with approximately 240 mL of water. For study purpose this food should be breakfast. Patient identification is part of the IMP administration process. Experimental arms will not receive IMP on Day 15, only control arm will receive HRZE.
- E: Concomitant Medication: collected from 14 days prior to first dose of IMP.
- F: Adverse Events: Collected from first dose of IMP to Follow-Up visit.
- G: Eligibility Assessment: Continuous from screening to just prior to first IMP dose.
- H: EBA unit inpatient: admission, anytime from initial screening to day -2, whichever is in the participant's best interest.
- I: EBA unit inpatient: discharge.
- J: Randomisation: May occur any time after eligibility has been confirmed to just prior to first IMP dose.
- K: Spot or Overnight Sputum: A screening and the last positive sputum sample (if >7 days after treatment start) on *M.tb* culture will be retained by the mycobacteriology laboratory for possible future testing. These samples contain the mycobacterium genetic material only, no participant genetic material is retained.
- L: Spot or Overnight Sputum: For eligibility assessments.
- M: Overnight sputum: Collection will start in the afternoons at approximately 15h00 and continue for 16 hours ± 1 hour overnight. The 16-hour sputum sampling for each of the sampling days must be finished prior to the administration of the next morning's IMP. Collection will be paused for 1 hour after any RESP301 dose that overlaps with the overnight sample collection window where applicable. If sputum collection is paused, participants to drink a cup of water before restarting (section 5.3.2).

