5.3.2. Dosing Instructions

The methodology will be detailed in the Pharmacy Manual.

On the days of IMP dosing:

Inhaled RESP301 nebulisation:

- all treatment regimens:
 - each dose is to be given using freshly prepared admix solution i.e., inhalation of the RESP301 should start with [REDACTED]
 - on Day 1 only: a short acting beta agonist is to be administered before starting the nebulisation for each dose, within 30 minutes of RESP301 is suggested
 - inhalation of RESP301 should be completed within [REDACTED] of starting NEB, pauses may be taken during NEB if not tolerated. The NEB should be stopped during a pause to preserve the remaining IMP until restarted.
 - the first dose should be given in the morning
 - All dosing should occur at approximately the same time each day (window of \pm 1 hour of the IMP dose/s on Day 1).
- once or twice daily:
 - When dosing overlaps with overnight sputum sample collection, sputum collection should be paused during and for [REDACTED] the end of the neb. A cup ([REDACTED] [REDACTED]) of water should be taken after the neb is complete, and prior to continuation of overnight sputum sample to wash away any remaining RESP301 from the airway.
 - the first dose should be given at half dose (half of each vial)
- three times a day (alone or with HRZE):
 - the first 2 doses should be given at half dose (half of each vial)
 - this tds dosing will be [REDACTED] to prevent overnight disruption to participants and limit overlap of dosing and sputum sampling
- twice or three times a day (alone or with HRZE):
 - to ensure a dose does not affect any *M.tb* present in the overnight sputum sample, should a dose overlap with the overnight sample collection window, sputum collection is

to be paused for [REDACTED] completion of inhalation of the RESP301 dose. Should the participant need to expectorate sputum during this pause, this will occur into a separate container which will be destroyed. The participant is to drink a cup ([REDACTED]) of water after the neb is complete, and prior to continuation of overnight sputum sample collection

HRZE oral dosing (alone or with RESP301):

- to occur in the morning
- preferably with a full glass of water fasted [REDACTED] However, if gastrointestinal irritation occurs, the tablets may be taken with food.
- if aluminium containing antacids are taken, administer one hour after the HRZE tablet/s dose.

HRZE plus RESP301 three times a day

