22 JUL 2024

continue for 16 hours  $\pm$  1 hour overnight. The 16-hour sputum sampling for each of the sampling days must be finished prior to the administration of the next morning's IMP. Collection will be paused for 30 minutes after evening RES301 dose where applicable.

- J: Spot or Overnight Sputum: For eligibility assessments.
- K: Blood collection for Haematology, Chemistry, and urinalysis on day 1 must be done prior to first dose.
- L:  $\beta$ -HCG Serum Pregnancy Test: All female participants.
- M: Follow-up visit: a window of  $\pm$ 3 days allowed.
- N: EBA unit inpatient: discharge

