| DM            | AGE              | Age  | Numeric       | LONG   |
| DM            | SEX              | Sex  | Numeric       | LONG   |
| LB MICRO      | BBLCFU           | Baseline bacterial load. (average log10 CFU on days -2 and -1)               | Numeric       | LONG   |
| LB MICRO      | BBLTTP           | Baseline bacterial load. (average TTP on days -2 and -1)                     | Numeric       | LONG   |
| LB SAFETY     | HIV              | HIV  | Numeric       | LONG   |
| CX            | EXTENT           | Severity or extent of disease  | Character     | 200    |
| CX            | CAV              | Presence of cavitation   | Numeric       | LONG   |
| LB MICRO      | SQUAL            | Sputum quality   | Numeric       | LONG   |
| LB MICRO      | SVOL             | Sputum volume  | Numeric       | LONG   |
| LB MICRO      | COMMENT          | Comments from the Microbiology Laboratory associated with sample observation | Character     | 200    |
| SU            | SMOKING          | Smoking  | Character     | 200    |
| LB MICRO      | MBGENMTBULTRA    | Genexpert MTB/RIF ULTRA Detection.   | Numeric       | LONG   |
| LB MICRO      | MBGENMTBULTRAPos | Genexpert MTB/RIF ULTRA Detection Positivity.                                | Numeric       | LONG   |
| LB MICRO      | MBGENMTBULTRACYC | Genexpert MTB/RIF ULTRA Detection Cycle Threshold.                           | Numeric       | LONG   |
| RE SPIROMETRY | REFVC            | Spirometry Forced Vital Capacity Actual value.                               | Numeric       | LONG   |

RESP30X-EBA: Statistical Analysis Plan22 JUL 2024

|               |            |  |         |      |
|---------------|------------|--|---------|------|
| RE SPIROMETRY | REFVC1     | Forced Expiratory Volume in 1 Second Actual value. | Numeric | LONG |
| RE SPIROMETRY | REFEV1_FVC | Modified Tiffeneau-Pinelli index Actual value.     | Numeric | LONG |
| CV SPMET      | CVSPMET    | SpMet Measurement Highest value.                   | Numeric | LONG |
| LB SAFETY     | LBHGB      | Haemoglobin in Blood Plasma.                       | Numeric | LONG |
| LB SAFETY     | LBBASOA    | Basophils Absolute (ABS) in Blood Plasma.          | Numeric | LONG |
| LB SAFETY     | LBEOSA     | Eosinophils Absolute (ABS) in Blood Plasma.        | Numeric | LONG |
| LB SAFETY     | LBIGA      | Imm Granulocyte Absolute (ABS) in Blood Plasma.    | Numeric | LONG |

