#### 10.2.3 Other Safety Variables

##### Laboratory parameters

Laboratory safety tests are performed throughout the study. The data will be listed with values outside the normal range flagged and with the grade according to Common Terminology Criteria for Adverse Events (CTCAE) mentioned. The recorded values and the change from baseline will be summarized by treatment and time of collection. The assessment (normal/abnormal-NCS/ abnormal-CS as well as the grade according to CTCAE) will be summarized for haematology, blood chemistry, and urinalysis by treatment and time of collection.

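### The SAP takes the oldest pre-dose value as safety baseline, so laboratory and vital-sign changes are measured from Visit 1 screening instead of the Day 1 pre-dose value

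*SAP*

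**What the plan says.** SAP 10.1 sets one general rule. When a variable has more than one data point before trial medication, baseline "will be regarded as the first of these observations". No exception is given, and neither document defines a different safety baseline.

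The rule feeds planned outputs. For laboratory parameters, SAP 10.2.3 states: "The recorded values and the change from baseline will be summarized by treatment and time of collection". The same section calculates change from baseline for vital signs. The evaluations table in Protocol 1.2 also lists both as actual values and changes from baseline.

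The Protocol 1.3 flow chart schedules the row "Safety labs (Haematology, Chemistry, Urinalysis)" at Visit 1 and on Day 1, and vital signs at Visit 1, Day -2, Day -1 and Day 1. Its footnote C reads: "Vital signs, safety laboratory: on days where there is IMP dosing, to be performed pre-dose". SAP Table 5, footnote K, agrees for the laboratory samples: "Blood collection for Haematology, Chemistry, and urinalysis on day 1 must be done prior to first dose".

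The Protocol synopsis adds, under the laboratory exclusion limits: "Investigations may be repeated once during screening if the initial result is unfavourable".

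For the bacteriology, the dataset specification in SAP 7.1 uses another definition: "Baseline bacterial load. (average TTP on days -2 and -1)", and likewise for log10 CFU.

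**The concern.** A safety baseline should describe the participant immediately before exposure. The plan collects such a value on Day 1 and then passes over it for the oldest one. Three things follow.

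1. Any shift between Visit 1 and Day 1, before any study drug, is carried into every later change.
2. The Day 1 sample is pre-dose, yet the shell for Table 14.3.2.1.2 shows it as the first change-from-baseline row.
3. For laboratory tests with an eligibility limit, a participant whose first result was unfavourable and who entered on the repeat has the failing result as baseline. Later values then look improved with no treatment effect. This does not apply to vital signs, which have no numeric eligibility limit.

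Separately, 10.1 does not exempt TTP and CFU, so the SAP holds two baseline rules for them. Only the descriptive Table 14.1.9 is left unclear.

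At stake is the meaning of the change tables and of individual changes. The protocol otherwise anchors safety at first dose: adverse events are collected from then, and under Protocol 7.1 a pre-existing abnormality that does not worsen is not an adverse event.

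**Working it through.** The plan gives no figure to reproduce. The check applies the rule to the schedule and then sizes the effect under stated assumptions.

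**Timing.** The 37-day maximum in the synopsis is 9 screening days plus 28, which implies no Day 0. Visit 1 (Day -9 to -3) is therefore 3 to 9 days before Day 1.

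| Variable | Scheduled pre-dose values | Baseline under 10.1 | Last pre-dose value |
|---|---|---|---|
| Safety laboratory | 2 (Visit 1, Day 1) | Visit 1 | Day 1 |
| Vital signs | 4 (Visit 1, Day -2, Day -1, Day 1) | Visit 1 | Day 1 |
| SpMet | 1 (its Day 1 measurement begins at the start of treatment) | Screening | Screening |

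**Drift.** Change from Visit 1 equals change from Day 1 plus the shift from Visit 1 to Day 1. A mean shift of d SD therefore adds d SD to every later row. The documents give no d; I assume 0.1 to 0.3 SD. For comparison, with reliability r (also assumed), the standard error of an arm's mean change at n = 15 is √(2(1 − r)/15):

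- r = 0.6: √(0.8/15) = 0.23 SD
- r = 0.8: √(0.4/15) = 0.16 SD
- r = 0.9: √(0.2/15) = 0.12 SD

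Drift of the assumed size is comparable with the sampling error of the figure reported.

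**Repeat entrants.** Simulation of 4 million subjects with unit total SD, no true change and independent errors. A subject enrols if the first value is at or below the cut-off, or if the first is above and the repeat is at or below. Day 1 plays no part in selection. The cut-offs in SD units are assumptions; lower limits behave as mirror images.

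| Cut-off (SD) | Share of enrolled on a repeat, r = 0.6 / 0.8 / 0.9 | Their mean change from the first value (SD) |
|---|---|---|
| 1.645 | 3.5% / 2.6% / 1.9% | -0.95 / -0.58 / -0.37 |
| 2.0 | 1.7% / 1.3% / 1.0% | -1.05 / -0.62 / -0.39 |
| 2.5 | 0.5% / 0.4% / 0.3% | -1.20 / -0.70 / -0.42 |

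- Measured from Day 1, the mean change in the same participants is 0 to within simulation error.
- Measured from the repeat value, it is +0.25 / +0.24 / +0.20 SD at the 1.645 cut-off.
- Per arm of 15 and per test, repeat entrants number 15 × 1.9% = 0.3 to 15 × 3.5% = 0.5 people at 1.645 SD, and under 0.1 at 2.5 SD.
- Over everyone enrolled, mean change from the first value moves by less than 0.01 SD at every setting.

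**The case against.** **The drift is visible.** With the Visit 1 baseline, the Day 1 row shows the pre-drug shift. Mean change since Day 1 can be recovered by subtracting it from a later row, if the participants are the same. The shell also agrees with the SAP's own rule. This stands for means, and the Day 1 row is better read as a consequence of the rule than as a second error. It does not correct later rows, and spreads, quartiles and individual changes from Day 1 cannot be recovered from the summary tables.

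**Nothing decisive uses this baseline.** Progression and amendment criteria rest on the TTP slope and adverse-event grades, laboratory adverse events rest on investigator judgement, and the study tests no hypothesis. All of this is true, and it keeps the point below the most serious level. Drift is expected to be equal across arms randomised in the same stage. That does not cover RESP301 tds alone, enrolled only in Stage 1, against the arms enrolled only in Stage 2.

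**The magnitudes are assumed.** They are. The actual limits are wide (for example, ALT above 3 × ULN), so the 2.5 SD row may be nearest: less than one repeat entrant per test is expected in all 75 participants (75 × 0.5% = 0.4).

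**Day 1 values may also select.** Flow chart footnote G keeps eligibility open until first dose. If Day 1 values were screened at the same cut-off, a Day 1 baseline would leave +0.11 to +0.20 SD in repeat entrants. The present rule gives -0.44 to -1.27 SD in those same participants.

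**The bronchodilator complicates vital signs.** For the RESP301 arms, Protocol 5.3.2 says: "on Day 1 only: a short acting beta agonist is to be administered before starting the nebulisation for each dose". Footnote C requires only that vital signs precede the IMP, and the documents do not show that their order relative to the bronchodilator is recorded. This stands as a condition on the fix. Day -1 readings exist as a fallback, so no new data are needed.

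**Conclusion.** The concern holds. The rule is explicit, no other passage overrides it, and it gives a less meaningful safety change than data the trial already collects. The change should be made.

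The size is modest. Drift enters the change tables one for one, but its magnitude is unknown; 0.1 to 0.3 SD is an assumption. The distortion for a repeat entrant is about -0.4 to -1.2 SD across the assumed cut-offs and reliabilities. It touches at most a few per cent of participants per test and hardly moves arm means. Recorded values, out-of-range flags, CTCAE grades and clinical-significance assessments are still reported, so no abnormal result is hidden. The primary EBA slope and SpMet are not affected. The TTP and CFU discrepancy is one of wording and concerns only Table 14.1.9.

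**What to change.** - In SAP 10.1, define the safety baseline as the last non-missing value before the first study medication: the Day 1 pre-dose value where taken, otherwise the latest screening or repeat value.
- For vital signs, require a reading taken before any Day 1 bronchodilator. Otherwise baseline heart rate could differ between the RESP301 arms and HRZE alone. Where the order cannot be established, use Day -1, preferably in every arm so that the definition stays common.
- Remove the pre-dose Day 1 row from the change-from-baseline shells.
- State in 10.1 that baseline TTP and log10 CFU are the means of Days -2 and -1, as in SAP 7.1, so that Table 14.1.9 agrees.

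The cost is a short SAP edit and a change of derivation, with no new data. One limit should be recorded: where Day 1 is missing and the repeat laboratory value serves as baseline, a smaller opposite shift remains (+0.20 to +0.25 SD at the 1.645 SD cut-off).
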